6.5 Follow-up (2 Weeks and 4 Weeks After End of Antifungal Treatment)

6.5.1 Follow-up 2 Weeks After End of Antifungal Treatment (+2 Days)

The following procedures will be performed at the Follow-up visit 2 weeks (+2 days) after EOT:

- Record vital signs, including temperature, blood pressure, heart rate, respiratory rate, oxygen saturation, and weight
- Intravascular catheter management log as clinically indicated
- Perform clinical laboratory assessments (serum chemistry, hematology, coagulation, and urinalysis)
- Perform urine pregnancy test (for females of childbearing potential only)

- Perform focused, symptom-based physical examination including a neurological examination
- Collect blood culture for *Candida* spp.
- Collect plasma sample for PK (APX001 [prodrug] and APX001A [active moiety])
- Collect other cultures and histopathology from other sites, as clinically indicated to monitor the site(s) and extent of candidemia infection
- Perform imaging tests as clinically indicated to monitor the site(s) and extent of candidemia infection
- Evaluate treatment outcome
- Record concomitant medications
- Assess adverse events

6.5.2 Follow-up 4 Weeks After End of Antifungal Treatment (+4 Days)

The following procedures will be performed at the Follow-up visit 4 weeks (+4 days) after EOT:

- Record vital signs, including temperature, blood pressure, heart rate, respiratory rate, oxygen saturation, and weight
- Intravascular catheter management log as clinically indicated
- Perform dilated fundoscopic examination (only required in those patients who had positive fundoscopic findings at Screening, or as clinically indicated)
- Perform clinical laboratory assessments (serum chemistry, hematology, coagulation, and urinalysis)
- Perform 12-lead ECG
- Perform urine pregnancy test (for females of childbearing potential only)
- Perform focused, symptom-based physical examination including a neurological examination
- Collect blood culture for *Candida* spp.
- Collect other cultures and histopathology from other sites, as clinically indicated to monitor the site(s) and extent of candidemia infection
- Perform imaging tests as clinically indicated to monitor the site(s) and extent of candidemia infection
- Evaluate treatment outcome
- Record concomitant medications
- Assess adverse events

6.6 Early Termination Visit and Withdrawal Procedures

For patients who are withdrawn from the study prior to completion, all EOT procedures will be performed at an Early Termination Visit. These procedures include the following:

- Record vital signs, including temperature, blood pressure, heart rate, respiratory rate, oxygen saturation, and weight
- Intravascular catheter management log
- Perform dilated fundoscopic examination (only required in those patients who had positive fundoscopic findings at Screening, or as clinically indicated)
- Perform clinical laboratory assessments (serum chemistry, hematology, coagulation, and urinalysis)
- Perform 12-lead ECG
- Perform urine pregnancy test (for females of childbearing potential only)
- Perform focused, symptom-based physical examination including a neurological examination
- Collect blood culture for *Candida* spp. and blood for *Candida* spp. testing by T2MR assay
- Collect plasma sample for PK (APX001 [prodrug] and APX001A [active moiety])
- Collect other cultures and histopathology from other sites, as clinically indicated to monitor the site(s) and extent of candidemia infection
- Perform imaging tests as clinically indicated to monitor the site(s) and extent of candidemia infection
- Collect serum sample for analysis of (1,3)- β -D-glucan
- Evaluate treatment outcome
- Record concomitant medications
- Assess adverse events

7 EFFICACY ASSESSMENTS

7.1 Primary Efficacy Endpoint

The primary efficacy parameter is Treatment Success at EOST as determined by the Data Review Committee (DRC).

7.2 Secondary Efficacy Endpoints

The secondary efficacy parameters include the following:

- Time to first negative blood culture
- Percentage of patients with Mycological Outcomes at EOST, EOT, and 2 and 4 weeks after EOT
- Percentage of patients with Treatment Success at EOT, and 2 and 4 weeks after EOT as determined by the DRC
- Overall survival at Study Day 30
- Number of patients with TEAEs

7.3 Exploratory Efficacy Endpoints

The exploratory efficacy parameters include the following:

- Change in serum (1,3)- β -D-glucan levels from Baseline (pre-dose) to EOST
- Correlation of blood culture and T2MR assay *Candida* spp. results from Baseline (pre-dose) through EOST

7.4 Definitions for Efficacy Assessments

7.4.1 At End of Study Drug Treatment (EOST)

Treatment Success is defined as meeting all of the following criteria:

- Two consecutive blood cultures negative for *Candida* spp.
- Alive at EOST
- No concomitant use of any other systemic antifungal therapies through EOST

Treatment Failure is defined as any case that does not meet the criteria for Treatment Success.

Mycological Outcome:

- Eradication is defined as a negative blood culture(s) for *Candida* spp. in the absence of concomitant antifungal therapy through EOST.

7.4.2 At End of Antifungal Treatment (EOT)

After completion of 14 days study drug therapy, if further antifungal treatment is indicated to complete treatment of candidemia in accordance with standard practice guidelines, fluconazole (unless susceptibility results warrant alternative antifungal therapy) may commence for up to a

further 7 days. If applicable, an assessment of efficacy will also be made at the end of this antifungal treatment at EOT.

Treatment Success is defined as meeting all of the following criteria:

- Two consecutive blood cultures negative for *Candida* spp.
- Alive at EOT
- No additional systemic antifungal therapies (except for protocol-allowed step-down treatment [e.g., fluconazole]) through EOT

Treatment Failure is defined as any case that does not meet the criteria for Treatment Success.

Mycological Outcome:

- Eradication is defined as a negative blood culture(s) for *Candida* spp. in the absence of additional antifungal therapy (except for protocol-allowed step-down treatment [e.g., fluconazole]) through EOT.

7.4.3 At Follow-up (2 Weeks and 4 Weeks After End of Antifungal Treatment)

- Recurrence (mycological) is defined as a mycologically confirmed infection based on blood culture with the same Baseline *Candida* spp. during the 4 weeks after EOT.
- Relapse (DRC Assessment) is defined as re-occurrence of *Candida* in blood culture during the Follow-up Period, or diagnostic parameters indicative of recurrence or late spread of the *Candida* infection.

7.5 Microbiological Assessments

7.5.1 Blood Cultures

A blood culture positive for *Candida* spp. drawn within 96 hours of APX001 dosing is required for eligibility as part of SOC. During screening, 2 consecutive sets (1 aerobic and 1 anaerobic blood culture bottle per set) of blood cultures from 2 separate sites (1 from a CVC and 1 peripheral venipuncture, or 2 peripheral venipunctures, if a CVC is not applicable) are required before the initiation of APX001 dosing. The screening cultures may be drawn on the day of dosing. Blood cultures (minimum of 1 set) for *Candida* spp. will also be performed at Baseline (pre-dose), during Study Drug Treatment, at EOST, EOT, and 2 and 4 weeks after EOT, or Early Termination. During the Study Drug Treatment Period, daily blood cultures are required on Study Days 1 through 4; thereafter, blood cultures may be stopped after negative results on 2 consecutive days are obtained. *Candida* spp. isolates from the blood cultures performed at the local laboratory must be submitted to the mycology reference laboratory for confirmation of identification and susceptibility testing.

If a Sponsor-approved rapid diagnostic test for candidemia is used to identify potentially eligible patients, subsequent confirmatory blood cultures are required prior to dosing. Likewise, *Candida* spp. isolates from these blood cultures are to be submitted to the mycology reference laboratory. Results from any further rapid diagnostic tests performed as per local SOC must be captured in the eCRF.

7.5.2 Cultures From Other Sites of Infection

Any *Candida* spp. cultured from a normally sterile site, from intravascular catheter tip(s), or from a sample indicative of deep-seated invasive Candidiasis discovered after dosing with APX001, should be sent to the mycology reference laboratory for confirmation of identification and susceptibility testing.

7.5.3 *Candida* Spp. Testing by T2 Magnetic Resonance Assay

Each time a blood culture is collected for the protocol, an additional blood sample will be collected for *Candida* spp. testing by T2MR assay at Baseline, during Study Drug Treatment, and through EOST or Early Termination. A central laboratory will perform the T2MR assay.

7.5.4 Intravascular Catheter Management and Log

If possible, all indwelling intravascular catheters should be removed and the catheter tips cultured prior to starting APX001 dosing. The entrance site should also be cultured if it appears infected. Intravascular catheter management should be managed at the site level as per local SOC.

8 SAFETY ASSESSMENTS

8.1 Adverse Events

An adverse event is defined as any untoward medical occurrence in a clinical investigation patient administered a pharmaceutical product, which does not necessarily have a causal relationship with this treatment. An adverse event can therefore be any unfavorable and/or unintended sign (including an abnormal laboratory finding), symptom, or disease temporally associated with the use of a study drug, whether or not related to the study drug. All adverse events, including observed or volunteered problems, complaints, or symptoms, are to be recorded on the appropriate eCRF.

Adverse events, which include clinical laboratory test variables, will be monitored and documented from the time of informed consent until study participation is complete. Patients should be instructed to report any adverse event that they experience to the Investigator. Beginning with Day 1 of study drug, Investigators should make an assessment for adverse events at each visit and record the event on the appropriate adverse event eCRF.

Wherever possible, a specific disease or syndrome rather than individual associated signs and symptoms should be identified by the Investigator and recorded on the eCRF. However, if an observed or reported sign or symptom is not considered a component of a specific disease or syndrome by the Investigator, it should be recorded as a separate adverse event on the eCRF. Additionally, the condition that led to a medical or surgical procedure (e.g., surgery, endoscopy, tooth extraction, or transfusion) should be recorded as an adverse event, not the procedure.

Any medical condition already present at Screening should not be reported as an adverse event unless the medical condition or signs or symptoms present at Baseline change in severity or seriousness at any time during the study. In this case, it should be reported as an adverse event.

Clinically significant abnormal laboratory or other examination (e.g., ECG) findings that are detected during the study or are present at Screening and significantly worsen during the study should be reported as adverse events. The Investigator will exercise his or her medical and scientific judgment in deciding whether an abnormal laboratory finding or other abnormal assessment is clinically significant. Clinically significant abnormal laboratory values occurring during the clinical study will be followed until repeat tests return to normal, stabilize, or are no longer clinically significant. Any abnormal test that is determined to be an error does not require reporting as an adverse event. A laboratory finding that is abnormal but not clinically significant (e.g., does not warrant intervention) is not considered an adverse event.

8.1.1 Adverse (Drug) Reaction

All noxious and unintended responses to a study drug related to any dose should be considered an adverse drug reaction. “Responses” to a study drug means that a causal relationship between a study drug and an adverse event is at least a reasonable possibility, i.e., the relationship cannot be ruled out.

8.1.2 Unexpected Adverse Drug Reaction

An unexpected adverse drug reaction is defined as an adverse reaction, the nature or severity of which is not consistent with the applicable product information. For APX001, the reference safety information is included in the Investigator’s Brochure (IB) currently in force. The reference safety

information will be reviewed yearly and the periodicity of the review will be harmonized with the reporting period of the Development Safety Update Report.

8.1.3 Assessment of Adverse Events by the Investigator

The Investigator will assess the severity (intensity) of each adverse event and will also categorize each adverse event as to its potential relationship to study drug using the categories of “yes” or “no.”

Assessment of Severity:

The severity of all adverse events should be graded according to the Common Terminology Criteria for Adverse Events (CTCAE) v4.03. These criteria can be found at <http://ctep.cancer.gov/reporting/ctc.html>. For those adverse events not listed in the CTCAE, the following grading system should be used:

- Mild (CTCAE Grade 1): Transient symptoms, awareness of sign/symptom, but easily tolerated and no interference with patient’s daily activities
- Moderate (CTCAE Grade 2): Marked signs/symptoms that interfere with patient’s usual activities, but still acceptable
- Severe (CTCAE Grade 3): Incapacitating signs/symptoms which cause considerable interference with the patient’s daily activities, unacceptable
- Life-threatening (CTCAE Grade 4): Life-threatening or disabling adverse event
- Death (CTCAE Grade 5): Death-related adverse event

The severity of infusion site reactions adverse events will be graded using the definitions in Table 1.

Table 1. Infusion Site Reaction Adverse Event Severity Grading Table

Event	Grade 1 (Mild)	Grade 2 (Moderate)	Grade 3 (Severe)	Grade 4 (Life-Threatening)
Infusion/injection site reaction	Tenderness with or without associated symptoms (e.g., warmth, erythema, itching)	Pain; lipodystrophy; edema; phlebitis	Ulceration or necrosis; severe tissue damage; operative intervention indicated	Life-threatening consequences; urgent intervention indicated
Infusion/injection site reaction is defined as a disorder characterized by an intense adverse reaction (usually immunologic) developing at the site of an infusion/injection.				

Causality Assessment:

The relationship of an adverse event to the administration of the study drug is to be assessed according to the following definitions:

No (unrelated, not related, no relation) – The time course between the administration of study drug and the occurrence or worsening of the adverse event rules out a causal relationship and another cause (concomitant drugs, therapies, complications, etc.) is suspected.

Yes (related) – The time course between the administration of study drug and the occurrence or worsening of the adverse event is consistent with a causal relationship and no other cause (concomitant drugs, therapies, complications, etc.) can be identified.

The definition implies a reasonable possibility of a causal relationship between the event and the study drug. This means that there are facts (evidence) or arguments to suggest a causal relationship.

The following factors should also be considered:

- The temporal sequence from study drug administration-
 - The event should occur after the study drug is given. The length of time from study drug exposure to event should be evaluated in the clinical context of the event
- Underlying, concomitant, intercurrent diseases-
 - Each report should be evaluated in the context of the natural history and course of the disease being treated and any other disease the patient may have
- Concomitant drug-
 - The other drugs the patient is taking or the treatment the patient receives should be examined to determine whether any of them might be recognized to cause the event in question
- Known response pattern for this class of study drug-
 - Clinical and/or preclinical data may indicate whether a particular response is likely to be a class effect
- Exposure to physical and/or mental stresses-
 - The exposure to stress might induce adverse changes in the recipient and provide a logical and better explanation for the event
- The pharmacology and PK of the study drug-
 - The known pharmacologic properties (absorption, distribution, metabolism, and excretion) of the study drug should be considered

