7.5.1. Adverse Events

AEs will be captured from the date of informed consent through study completion. All AEs will be coded to system organ class and preferred term using the MedDRA, Version 20.1. TEAEs are defined as AEs that start on or after the administration of study drug.

An overview of AEs will be provided including counts and percentages of patients (and event counts) with the following:

- Any AEs;
- Any TEAEs (overall and by maximum severity);

- Any study drug-related TEAEs (overall and by maximum severity);
- Any serious AEs (SAEs);
- Any treatment-emergent SAEs (TESAEs);
- Any study drug-related treatment-emergent SAEs (TESAEs);
- Any TEAEs leading to discontinuation of study drug;
- Any study drug-related TEAEs leading to discontinuation of study drug;
- Any AEs leading to discontinuation of study;
- Any study drug-related TEAEs leading to discontinuation of study; and
- Any AEs leading to death.

The number and percentage of patients who experienced at least one TEAE will be presented by system organ class and preferred term. Drug-related TEAEs, study drug withdrawals due to TEAEs, and all SAEs will be summarized in the same manner.

Summaries will be provided by worst grade for the number and percentage of patients with TEAEs and for patients with drug-related TEAEs by system organ class and preferred term.

Although a patient may have two or more TEAEs, the patient is counted only once within a System Organ Class and Preferred Term category. The same patient may contribute to two or more preferred terms in the same System Organ Class category or to two different System Organ Class categories.

A list of patients who have serious adverse events (SAEs), a list of patients who discontinue from study drug due to TEAEs, and a list of death due to AEs will be provided. All adverse events will be listed.

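### The yes/no causality definitions in Protocol 8.1.3 are not complements, so an event with plausible timing and another possible cause has no defined code, although 8.1.1 can make it an adverse reaction.

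*Protocol*

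**What the plan says.** Under Protocol 8.1.3 the investigator "will also categorize each adverse event as to its potential relationship to study drug using the categories of" yes or no. There is no third category.

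- *Yes* applies where the time course "is consistent with a causal relationship and no other cause (concomitant drugs, therapies, complications, etc.) can be identified".
- *No* applies where the time course "rules out a causal relationship and another cause (concomitant drugs, therapies, complications, etc.) is suspected".

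Directly after the *Yes* definition the section adds: "The definition implies a reasonable possibility of a causal relationship between the event and the study drug". It then lists factors to weigh, among them other diseases, concomitant drugs and pharmacology; for example, "Each report should be evaluated in the context of the natural history and course of the disease being treated".

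Protocol 8.1.1 sets its own standard. An untoward response is an adverse drug reaction when "a causal relationship between a study drug and an adverse event is at least a reasonable possibility, i.e., the relationship cannot be ruled out".

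The code is used in three places. Protocol 9.2.2 tabulates TEAEs by relationship. SAP 7.5.1 has several drug-related lines, the first of which begins "Any study drug-related TEAEs (overall and by maximum severity", and gives no definition of related. Protocol 8.3 requires all SAEs to be reported up to 30 days after the last dose, and after that only those the investigator considers related.

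**The concern.** Each definition in 8.1.3 joins two conditions with an *and*, so one is not the negation of the other. The case that matters is an event whose timing fits the drug but which also has another possible cause.

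That case should be expected here. The consent provisions (Protocol 6.1) foresee septic shock, mechanical ventilation and sedation, and SAP 7.3.3 summarises APACHE II and ICU status. Such patients will often have a competing explanation for an event. Protocol 1.2 reports that gastrointestinal and nervous system TEAEs increased between 300 mg and 600 mg IV in Phase 1, and in acutely ill patients such symptoms can have other causes too.

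Safety is part of the primary objective and there is no control arm to show the background event rate. Investigator attribution is therefore the main planned way to separate drug effects from background. If two investigators can code the same event differently, each with support in the text, the drug-related tables depend partly on which sentence each one followed.

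**Working it through.** The plan gives no figure to reproduce. The check is a truth table of timing against other cause, scored on the literal text.

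| Timing | Other cause | Literal *Yes* (8.1.3) | Literal *No* (8.1.3) | Reaction under 8.1.1 |
|---|---|---|---|---|
| Consistent | None | Met | Not met | Yes |
| Consistent | Possible | Not met | Not met | Yes, if the drug cannot be excluded |
| Ruled out | Suspected | Not met | Met | No |
| Ruled out | None | Not met | Not met | No |

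1. Two of the four combinations have no literal code. The last row is harmless, because once timing excludes the drug the obvious answer is *No*.
2. The second row carries the conflict. The event fails *Yes* because another cause can be identified. It equally fails *No* because timing does not exclude the drug. Both 8.1.1 and the reasonable-possibility sentence in 8.1.3 point towards related.
3. The SAP does not settle it. A relationship left blank is queried under Protocol 10.1.5. If it stays blank, SAP 7.1.2 does not impute it, so the event is not counted as related.

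**Outputs that use the code.** The overview in SAP 7.5.1 has 11 lines. Four are drug-related: TEAEs, treatment-emergent SAEs, TEAEs leading to discontinuation of study drug, and TEAEs leading to discontinuation of study. Two further tables are drug-related: incidence, and worst grade, each by system organ class and preferred term.

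**Scale, as an illustration.** Input: about 20 patients (Protocol 9.2.6). Assumption: *m* patients whose only possibly related event in a given line is of the second-row type and is not coded *Yes*. Change in that line = *m*/20.

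- *m* = 1: 1/20 = 5 percentage points
- *m* = 2: 2/20 = 10 points
- *m* = 3: 3/20 = 15 points
- If such events are coded *Yes*: 0 points

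Each event not coded *Yes* lowers the drug-related event count by 1. Patient percentages move less readily. In the class and term tables "the patient is counted only once within a System Organ Class and Preferred Term category", and a patient with another related event stays in an overview line. In the severity rows such a patient may stay in the line but move to a lower maximum grade. The documents do not give *m*.

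**Late SAEs.** The duty in Protocol 8.3 to report related SAEs after 30 days has no end date. Routine adverse event capture stops when participation ends (Protocol 8.1, SAP 7.5.1). From then on, an SAE that is not judged related has no second route into the data.

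**The case against.** The strongest reply is that 8.1.3 is softer than its two definitions. It speaks of a reasonable possibility, asks for facts or arguments that suggest causality, and lists factors that invite comparative judgement. An investigator can properly record *Yes* for a mixed event, or *No* where natural history or a concomitant drug explains it better. Protocol 11.5 also has eCRF completion procedures reviewed with sites before enrolment. Those procedures are not among the documents and may already resolve the matter. This stands as far as it goes: actual coding practice is unknown, and not every mixed event coded *No* is an error. It does not remove the defect, because the softer sentence leaves the no-other-cause condition in force beside it and nothing says which governs.

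A reader might infer that drug-related counts will definitely be understated. The documents do not support that. A literal reader who must choose could just as well reject *No*, since its timing condition also fails. Under-counting against the 8.1.1 standard follows only where *No* or a blank is recorded.

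A second reply is that little can be excluded in acutely ill patients, so a standard of not being able to rule the drug out could make the related count less informative. This is a fair cost, and a reason to keep the listed factors as guidance.

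Finally, the study is small and descriptive, a DSMB reviews accumulating data, and all adverse events are listed. That limits the weight of the point but does not make the rule consistent.

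**Conclusion.** The point holds as an internal inconsistency. One of the four timing-by-cause combinations has no valid code in 8.1.3 while 8.1.1 can make it a reaction, and the SAP does not resolve it. The consequence is undefined coding that may vary between investigators, with under-counting wherever the no-other-cause condition is applied and the event is recorded as *No* or left blank.

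It reaches 4 of 11 overview lines, 2 drug-related tables and the tabulation by relationship in Protocol 9.2.2. The 5 points per patient is only an illustration: it assumes a denominator of 20 and a patient with no other related event in that line. The net effect cannot be estimated from the documents.

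A reader might also suppose that late SAE reporting is affected only in its route, or only for the few days of participation left after the 30-day period. That is not supported, because the duty for related SAEs is open-ended and outlasts routine capture.

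All-causality tables are not affected, including the secondary endpoint that counts patients with TEAEs (Protocol 7.2, SAP 6.2). The wording should be corrected, but it does not threaten the efficacy analysis.

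**What to change.** Reconcile Protocol 8.1.3 with 8.1.1:

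- Define *Yes (related)* as a reasonable possibility that study drug caused or contributed to the event, even if another cause is also possible.
- Define *No* as everything else, so that each event has exactly one code.
- Keep the listed factors as guidance for that judgement.
- Repeat the definition in SAP 7.5.1.
- Re-assess events already coded under the present wording, or flag them in the listings.

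The cost is a protocol amendment with the full review and approval required by Protocol 12.1, short guidance to sites, and one or two sentences in the SAP. The related count will be less specific and may look less favourable; the all-causality tables remain beside it for context. No endpoint or sample size changes.
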